23.1. Subject study completion

The minimum duration of each subject's participation is approximately one month from the MRI scan (1-Month Post Scan visit). When the subject's participation in the clinical study has been completed the subject will return to standard medical care as per physician's recommendation.

Appendix A: Definitions

Non-study Specific Definitions

Adverse Event (AE)

Any untoward medical occurrence, unintended disease or injury, or untoward clinical signs (including abnormal laboratory findings) in subjects, users or other persons, whether or not related to the investigational medical device under clinical investigation.

Note 1: This definition includes events related to the medical device under investigation or the comparator.

Note 2: This definition includes events related to the procedures involved.

Note 3: For users or other persons, this definition is restricted to events related to medical devices under investigation

Serious Adverse Event (SAE)

If the AE meets any of the criteria below, it is regarded as a serious adverse event (SAE).

- a) Led to a death,
- b) Led to a serious deterioration in health of the subject, that either resulted in
 1. a life-threatening illness or injury, or
 2. a permanent impairment of a body structure or a body function, or
 3. in-patient hospitalization or prolongation of existing hospitalization, or
 4. medical or surgical intervention to prevent life threatening illness or injury or permanent impairment to a body structure or a body function.
 5. chronic disease
- c) Led to fetal distress, fetal death or a congenital abnormality or birth defect.

Note: A planned hospitalization for pre-existing condition, or a procedure required by the CIP, without a serious deterioration in health, is not considered to be an SAE.

Adverse Device Effect (ADE)

An adverse event related to the use of an investigational medical device.

This definition includes adverse events resulting from insufficient or inadequate instructions for use, deployment, implantation, installation, or operation, or any malfunction of the investigational medical device.

This definition includes any event resulting from the use error or from intentional misuse of the investigational medical device.

Serious Adverse Device Effect (SADE)

Adverse device effect that has resulted in any of the consequences characteristic of a serious adverse event.

Unanticipated Adverse Device Effect (UADE)

As defined in 21 CFR §812.3, unanticipated adverse device effects (UADE) are defined as any serious adverse effect on health or safety or any life-threatening problem or death caused by, or associated with, a device, if that effect, problem, or death was not previously identified in nature, severity, or degree of incidence in the CIP or application (including a supplementary plan or application), or any other unanticipated serious problem associated with a device that relates to the rights, safety, or welfare of subjects.

Anticipated Serious Adverse Device Effect (ASADE)

A serious adverse device effect which by its nature, incidence, severity or outcome has been previously identified in the risk analysis report.

Unanticipated Serious Adverse Device Effect (USADE)

A serious adverse device effect which by its nature, incidence, severity or outcome has not been identified in the current version of the risk analysis report.

Complication

A complication is defined as an SADE that requires an invasive intervention or leads to death.

Device Deficiency (DD)

Device deficiency is defined as an inadequacy of a medical device related to its identity, quality, durability, reliability, safety or performance, such as malfunction, misuse or use error and inadequate labeling. This includes the failure of the device to meet its performance specifications or otherwise perform as intended. Note: Performance specifications include all claims made in the labeling of the device.

Device Malfunction

A failure of a device to meet its performance specifications or otherwise perform as intended, when used in accordance with the instructions for use or CIP.

Device Relationship

Determination of whether there is a reasonable possibility that an investigational product or device under investigation caused or contributed to an AE is to be determined by the Investigator and recorded on the appropriate CRF form. Determination should be based on assessment of temporal relationships, evidence of alternative etiology, medical/biologic plausibility, and patient condition (pre-existing condition).

Vulnerable Subject

Vulnerable subject is defined as individual whose willingness to volunteer in a clinical investigation could be unduly influenced by the expectation, whether justified or not, of benefits associated with participation or of retaliatory response from senior members of a hierarchy in case of refusal to participate.

The definition shall be applied by the investigator judgement to exclude individuals who are unable to fully understand all aspects of the investigation that are relevant to the decision to participate, or who could be manipulated or unduly influenced as a result of a compromised position, expectation of benefits or fear of retaliatory response.

Study Specific Definitions

Medical Device

Any instrument, apparatus, implement, machine, appliance, implant, software, material or other similar or related article

(a) Intended by the manufacturer to be used, alone or in combination, for human beings for one or more of the specific purpose(s) of

- Diagnosis, prevention, monitoring, treatments or alleviation of disease,
- Diagnosis, monitoring, treatment, alleviation of, or compensation for, an injury,
- Investigation, replacement, modification, or support of the anatomy or of a physiological process,
- Supporting or sustaining life,
- Control of conception,
- Disinfection of medical devices and

(b) Which does not achieve its primary intended action in or on the human body by pharmacological, immunological or metabolic means, but which may be assisted in its intended function by such means

MRI Scan Related Complication

A complication is deemed to be MRI related if it is caused by or related to the interaction between the ICD/ CRT-D system and the MRI system that occurs during the MRI scan and includes the time the subject is within the 5 Gauss line of the MRI system, or up through the subject's 1-month post MRI scan follow up visit. The MRI scan related complications will be based on the CEC adjudication data.

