2.2. Primary Endpoints

- Safety: Freedom from MRI-scan related complications related to the ICD/ CRT-D device and/or leads from the time of the MRI scan to 1-month post-MRI scan testing.
- Effectiveness: Proportion of leads with a capture threshold increase of $\leq 0.5V$ at 0.5ms for RA and RV leads and $\leq 1.0V$ at 0.5ms for LV leads from pre-MRI scan to 1-month post-MRI scan testing.
- Effectiveness: Proportion of leads with a sensing amplitude decrease of $\leq 50\%$ from pre-MRI scan testing to 1-month post-MRI scan.

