8.1.3. Measures for reducing and avoiding bias

Measures to reduce and avoid bias in this study include: allowing all subjects who meet the eligibility criteria specified in this CIP may be enrolled in this study, the Sponsor will approach sites for participation without bias or consideration for specific demographic subgroups; additionally, clinical events (adverse device effects and deaths) occurring after the MRI settings have been programmed, will be adjudicated by an independent Clinical Events Committee (CEC).

The CEC is an independent adjudication body comprised of qualified physicians who are not participants in the clinical investigation. The CEC will review and adjudicate pre-specified events reported by investigators or identified by Safety personnel for the clinical investigation as defined in the CEC charter and according to definitions provided in this CIP.

8.1.4. Investigational medical device and reference medical device/reference diagnosis/therapeutic method (if any)

Devices and reference numbers are listed in **Table 1: Study Device** above.

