8.3.1. Description of the safety endpoint

Freedom from MRI-scan related complications from the time of the MRI scan to 1-month post-MRI scan testing.

8.3.2. Selection of method and time for evaluation, recording and analysis of the safety endpoints

Since the objective is to evaluate the effect of MRI exposure for the ICD/ CRT-D device groups included in this study, the safety parameters were selected to include only MRI-scan related complications from the time of device programming for an MRI scan to 1-month post-MRI scan. An independent physician CEC will adjudicate all adverse device effects during this period to determine the relatedness to the MRI scan.

Safety surveillance within this study and the safety reporting, both performed by the investigator, starts as soon as the subject completes the pre-MRI visit testing and the MRI Settings have been programmed according to the protocol. The safety surveillance and the safety reporting will continue until the last study visit has been performed, the subject is deceased, the subject/investigator concludes his participation into the clinical study or the subject withdrawal from the clinical study.

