
*Note: When MRI Settings are enabled, sensing is disabled. Determine whether or not the subject requires pacing support during the MRI scan. When pacing support is needed, set the MRI Mode to the asynchronous pacing mode (VOO). When pacing support is not needed, set the MRI Mode to Pacing Off.
 
Some subjects may be susceptible to cardiac arrhythmia induced by competitive pacing when an asynchronous MRI Mode is selected. For these subjects, it is important to select an appropriate MRI pacing rate to avoid competitive pacing and then minimize the duration of the asynchronous pacing operation.
 
In MR Conditional ICDs, tachytherapy is disabled when the MRI settings are programmed. After the electrical measurements for the RA lead and/or RV lead have been taken, capacitor maintenance has been performed, the MRI Checklist (on the programmer) verified and the MRI Setting saved, activate the MRI parameters.
		

TABLE 6: MRI PARAMETERS- CRT-D

Parameters	Selectable Options	Nominal Values
MRI Mode*	DOO Pacing off	DOO
MRI Base Rate	30-100 bpm	85 bpm
MRI paced AV delay	25-120ms	120 ms
MRI RV Pulse Configuration	Bipolar	n/a
MRI RV Pulse Amplitude	5.0 V, 7.5V	n/a
MRI RV Pulse Width	1.0 msec	n/a
MRI V pacing chamber	RV only	RV only
Tachy settings	Disabled	Disabled

*Note: When MRI Settings are enabled, sensing is disabled. Determine whether or not the subject requires pacing support during the MRI scan. When pacing support is needed, set the MRI Mode to the dual chamber asynchronous pacing mode (DOO).
 
Some subjects may be susceptible to cardiac arrhythmia induced by competitive pacing when an asynchronous MRI Mode is selected. For these subjects, it is important to select an appropriate MRI pacing rate to avoid competitive pacing and then minimize the duration of the asynchronous pacing operation.
 
In MR Conditional CRT-Ds, tach therapy is disabled when the MRI settings are programmed.
 
After the electrical measurements for the RA lead and/or RV lead, and/or LV lead have been taken, capacitor maintenance has been performed, the MRI Checklist (on the programmer) verified and the MRI Setting saved, activate the MRI parameters.
		

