8.4.4.6. Post MRI scan testing

Device Assessment and Programming

Following the MRI Scan, remove the subject from the MRI bore. Interrogate the ICD/CRT-D. Disable the MRI Settings. **Note: MRI settings must be disabled to ensure that tachyarrhythmia therapy is turned back on.** Obtain the following for the study leads: Interrogate the ICD/ CRT-D, and obtain the following for the Study leads:

- In-clinic bipolar and unipolar* capture threshold at a pulse width of 0.5 ms. Either the manual decrement or automatic (in-clinic, programmer-based) method may be used to obtain the capture threshold.
- In-clinic bipolar sensing amplitude. Either the incremental or the automatic (in-clinic, programmer based) method may be used to obtain the sensing threshold.
- In-clinic atrial and ventricular bipolar and unipolar* lead impedance

**NOTE: Unipolar and bipolar configurations should be collected for LV leads*

***NOTE:** RV capture thresholds are not required to be obtained if a high ventricular rate is present. If available, sites should use the automatically obtained pacing capture threshold from the most recent archival data as a substitute for the in-clinic capture threshold. RV sensing measurements are not required if the subject's intrinsic rate is established to be ≤ 30 beats per minute.*

Reporting of MRI Scan-Related Adverse Events

An ADE or SADE related to the following should be reported as soon as possible, but no later than 24 hours after the site becomes aware of the event, to Abbott: clotting, pulmonary embolism, or heating of the device pocket during the MRI scan. These events are likely to be associated with symptoms occurring during or immediately following the MRI scan and may manifest as chest pain, shortness of breath, or changes in vital signs during or immediately following the MRI scan.

To ensure all ADEs or SADEs related to or caused by the MRI scan are appropriately captured, before starting the scan, verbally instruct the subject to report symptoms of chest

pain, shortness of breath or pocket discomfort that he/she experiences while being scanned or immediately after exiting the scanner. Note changes in vital signs such as changes in heart rate, room air blood oxygen saturation, and/or respiration rate that occur during the MRI scan that may suggest an ADE or SADE has occurred due to clotting, pulmonary embolus or related to lead tip or device pocket heating.

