16.1. Adverse events

To comply with worldwide standards and guidelines on clinical study adverse event reporting, the Sponsor has adopted uniform and worldwide applicable standard definitions and reporting timelines to be used and adhered to by the investigators.

Safety surveillance within this study and the safety reporting, both performed by the investigator, starts as soon as the subject's MRI Settings have been programmed during the MRI visit.

Adverse events will be monitored until they are adequately resolved, or the subject has ended his/her participation in the study, whichever comes first. The status of the subject's condition should be documented at each visit.

Reportable events shall be submitted to the Sponsor. The Sponsor will ensure that all applicable events and device deficiencies are reported to the relevant authorities as per regulations. The sites should notify the Sponsor of reportable adverse events by creating and saving the applicable CRF within the electronic data capture (EDC) system.

Additional information may be requested by the Sponsor to support the reporting of AEs to regulatory authorities. The investigator must notify the IRB/EC, if appropriate, in accordance with national and local laws and regulations, of the AEs reported to the Sponsor.

All study related adverse events will be reported as per applicable regulatory requirements. The Sponsor will also notify all the other medical institutions conducting the clinical study and Ethics committees of the occurrence of SAEs.

Unchanged, chronic, non-worsening or pre-existing conditions are not AEs and should not be reported.

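### The primary safety endpoint has two start times, and Appendix A does not settle whether a complication caused by the MRI settings counts

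*Combined protocol and SAP*

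**What the plan says.** **Start time.** Protocol 8.3.1 defines the endpoint as "Freedom from MRI-scan related complications from the time of the MRI scan to 1-month post-MRI scan testing". Protocol 2.2 and SAP 1.4.1 and 2.3.1 use the same opening, "from the time of the MRI scan to 1-month post-MRI scan testing". Protocol 8.3.2, which explains how the endpoint is evaluated, restricts it to MRI-scan related complications but counts them "from the time of device programming for an MRI scan to 1-month post-MRI scan".

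**Reporting and adjudication.** Section 16.1 starts safety reporting once the subject's "MRI Settings have been programmed during the MRI visit". Section 8.1.3 sends to the Clinical Events Committee (CEC) the "clinical events (adverse device effects and deaths) occurring after the MRI settings have been programmed".

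**Cause.** Appendix A defines a complication as a serious adverse device effect that needs an invasive intervention or leads to death. To qualify as MRI scan related, the complication must be one "caused by or related to the interaction between the ICD/ CRT-D system and the MRI system that occurs during the MRI scan". The definition takes in the time inside the 5 Gauss line and runs to the 1-month visit. It does not mention the MRI settings.

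**What the settings do.** The note to Table 5 in 8.4.4.4 states: "In MR Conditional ICDs, tachytherapy is disabled when the MRI settings are programmed". The note to Table 6 says the same of the CRT-Ds. Section 8.4.4.6 adds: "MRI settings must be disabled to ensure that tachyarrhythmia therapy is turned back on". Table 10 lists, under potential MRI related events, competitive pacing that could induce VT/VF while an ambulatory subject is paced asynchronously in MRI mode. Descriptive endpoint 6 (protocol 2.3, SAP 3.5) foresees delays in reprogramming after the scan.

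**The concern.** This is the only primary safety endpoint, and the study supports a labeling submission with a separate report for each device group (protocol section 20, SAP 2.6). Two things have to be fixed before an event can be classified: when the clock starts and which causes qualify.

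The clock has two stated starts. The event stream sent to the CEC opens at the earlier one, while the endpoint as defined in four of five places opens at the later one.

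The cause wording looks only at what the scanner does to the device. The investigational condition also includes the programmed settings, which can do harm without any scanner field: tachyarrhythmia therapy is off, and pacing may be asynchronous. If the wording is applied literally, a death or invasive intervention caused by the settings would be absent from the primary safety result, although the protocol's own risk table calls that kind of event MRI related.

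**Working it through.** No figure in the plan needs reproducing: SAP 2.4 states that no sample size or power calculation was done. The check is a comparison of passages, followed by an illustration of size.

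**Step 1. Combine the two windows with two readings of Appendix A.** The literal reading requires a device-scanner interaction. The broad reading lets the looser relatedness wording cover the settings.

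| Complication | Window from scan (2.2, 8.3.1, SAP 1.4.1, 2.3.1) | Window from programming (8.3.2) | Literal Appendix A | Broad Appendix A |
|---|---|---|---|---|
| Settings-caused, after programming and before the scan | Outside | Inside | Does not qualify | Qualifies |
| Settings-caused, during the scan | Inside | Inside | Does not qualify | Qualifies |
| Settings-caused, after the scan, settings still active | Inside | Inside | Does not qualify | Qualifies |
| Device-scanner interaction, during or after the scan | Inside | Inside | Qualifies | Qualifies |

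- Row 1 is where the start time matters. On the broad reading the event counts under 8.3.2 and not under the other four places. On the literal reading it fails on cause under both.
- Rows 2 and 3 do not depend on the start time; only the cause wording decides.
- Row 4 is unaffected.

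Aligning the start time alone therefore leaves rows 2 and 3 open, and amending Appendix A alone leaves row 1 open. The two changes are needed together.

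**Step 2. How long is the exposed time?** Table 4 puts pre-scan, scan and post-scan procedures on the same day, so the time with settings active is within one day if that rule is kept. The documents give no length in minutes or hours. Appendix A already covers time inside the 5 Gauss line, so the pre-scan gap is mainly from programming to that line.

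**Step 3. Illustration of size.** Inputs: 15 enrolled less 5 anticipated attrition = 10 evaluable per group (8.1.12); four groups give 4 × 10 = 40 evaluable or 4 × 15 = 60 enrolled. The interval is the two-sided exact 95% Clopper-Pearson that SAP 2.2.2 says may be presented. With all n subjects free of events, the lower limit is 0.025^(1/n). With one event, it is the 2.5% quantile of a Beta(n − 1, 2) distribution. The single event is an assumption; the documents give no expected rate.

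| n | No event (lower limit) | One event (lower limit) |
|---|---|---|
| 10 (one group, minimum) | 100% (69.2%) | 9/10 = 90.0% (55.5%) |
| 15 (one group, all enrolled) | 100% (78.2%) | 14/15 = 93.3% (68.1%) |
| 40 (four groups, minimum) | 100% (91.2%) | 39/40 = 97.5% (86.8%) |
| 60 (four groups, all enrolled) | 100% (94.0%) | 59/60 = 98.3% (91.1%) |

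**The case against.** The strongest reply is that the documents already lean towards inclusion. Appendix A accepts events related to, and not only caused by, the interaction. Table 10 files pacing in MRI mode under MRI related events. Classification rests with the CEC, which works to a charter and an adjudication form that were not supplied. SAP 2.1 and part of SAP 2.3.1 are blacked out. A rule may therefore exist outside the visible text. This stands as a limit on the consequence: nobody can say from these documents that such an event would in fact be excluded. It does not reconcile 8.3.1 with 8.3.2, and 8.3.2 asks the CEC only about relatedness to the scan.

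A second reply is that 8.3.2 gives the aim as the effect of MRI exposure, so a sponsor may legitimately confine the endpoint to device-scanner interaction. That also stands. The documents need one start time and a clear statement; they do not force the broader endpoint.

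Three stronger readings are tempting and are not supported:

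- *The rules also conflict after the scan.* They do not. Every passage has the window open then, and only the Appendix A wording is in question.
- *A subject whose settings were programmed but who was never scanned is withdrawn (Table 7) and leaves only vital status behind.* Section 14.6 does limit further data in general, but it also asks sites to attempt a final visit with device assessment, and to seek permission for further follow-up when withdrawal was for device safety or performance problems. Section 16.1.2 requires reportable events to be followed. Subjects who cannot tolerate the scan are not withdrawn at all (8.4.4.5).
- *The change from 100% to 90.0% measures this defect.* Any single event in a group of ten has that effect. It shows only how sensitive the reported rate is.

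**Conclusion.** The point holds as a defect of wording in the primary safety endpoint. The start-time conflict is certain, because all the passages concerned are visible current text. The attribution gap is a matter of reading: literal wording excludes settings-caused complications, while Table 10 and the relatedness wording point the other way.

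The practical size is small. The exposed time is short under the same-day rule, the event must be serious and lead to invasive intervention or death, and few such events are likely. SAP 2.7 sets no success criterion, so no pass or fail turns on it. An affected event would still appear in the adverse device effect or mortality summaries (SAP 3.2 and 3.5). What is at risk is the primary safety rate reported for a small group. The illustration rests on one assumed event and on 10 to 15 subjects per group.

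**What to change.** 1. State one start time in protocol 2.2, 8.3.1 and 8.3.2 and in SAP 1.4.1 and 2.3.1. Programming of the MRI settings is preferable, because reporting and adjudication already start there.
2. Amend Appendix A to say that a complication caused by or related to the MRI settings, from programming until they are disabled, counts as MRI scan related, in line with Table 10. Check that the CEC charter and adjudication form agree.
3. If the sponsor intends the narrower device-scanner endpoint, say so, bring 8.3.2 into line with the scan start, and report settings-related complications next to the primary endpoint.

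The cost is wording in up to four protocol places and two SAP places. No new visits or data are needed, and clinical procedures do not change. The downside of the broader definition is a possibly slightly less favourable rate.
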